6.5.1. Palliative Medicine and Supportive Care

The need for any form of radiotherapy (including palliative) in Cycles 1-2 will be cause for early discontinuation from the study. In Cycle 3 and beyond, palliative radiotherapy will be allowed if the parameters below are met.

Palliative radiation therapy is permitted after discussion with and agreement of the Lilly CRP/CRS or designee for irradiating small areas of painful metastases that cannot be managed adequately using systemic or local analgesics. Such areas must not be an identified target lesion and must not constitute progressive disease or meet RECIST/immuno-Response Evaluation Criteria in Solid Tumors (iRECIST) criteria for progressive disease. Any symptomatic deterioration or clinical disease progression requiring, in the opinion of the investigator, other forms of specific antitumor systemic therapy will be cause for discontinuation of study therapy.

In addition, any disease progression requiring other forms of specific antitumor therapy will also necessitate early discontinuation from the study. Appropriate documentation for all forms of

premedications, supportive care, and concomitant medications must be captured on the case report form (CRF). Replacement hormonal therapy initiated before study entry will be allowed.

Patients should receive full supportive care. Hematopoietic growth factors (eg, G-CSFs) may be administered according to institutional guidelines and the local Package Insert, except in the DLT observation period. Hematopoietic growth factors will be allowed in the DLT observation period if a patient experiences neutropenia that is declared an AE. Administration of G-CSFs prior to first occurrence of neutropenia is prohibited. Blood product transfusions are permitted throughout the study.

Prophylactic antibiotic treatment should be consistent with American Society of Clinical Oncology (ASCO) guidelines (Flowers et al. 2013).

If clinically indicated at any time during the study, erythropoietin and packed red blood cell transfusions may be used according to ASCO guidelines (Rizzo et al. 2008) with adherence to the local Package Insert. All concomitant medications should be recorded throughout the patient's participation in the study.

6.6. Dose Modification

Dose reductions are not allowed in this study.

No dose modification for either LY3435151 or pembrolizumab (delays or omissions greater than 14 days) is allowed during the DLT observation period (42 days for Cohorts A1-A6 and B1-B2). Starting at Cycle 3, dose delays will be permitted. See Section 7 for discontinuation criteria.

After the DLT observation period, doses of the LY3435151 or pembrolizumab may be delayed, omitted, or discontinued to manage specific AEs or other toxicities. All dose modifications should be documented, including the approach taken and a clear rationale for the need for modification. The investigator must assess whether the toxicity is at least possibly due to study treatments and apply the dose modification guidelines. Investigators are encouraged to consult Lilly for additional guidance.

A cycle is defined as an interval of 21 days as shown in the SoA (Section 1.3). A delay of a cycle due to holiday, weekend, bad weather, or other unforeseen circumstances will be permitted for a maximum of 7 days and not counted as a protocol deviation. The reason for the delay should be documented on the eCRF.

Starting at Cycle 3, if a patient requires a cycle delay for any safety reasons other than those above, study treatment should be resumed within 21 days, if possible and appropriate. In rare circumstances, a cycle delay of >21 days may be permitted before permanent treatment discontinuation, as long as the patient demonstrates clinical benefit, does not have objective progression, and is recovering from the toxicity. Longer delays may be allowed for irAEs, as described in Section 6.6.1. Such circumstances must be discussed with the Lilly CRP/CRS.

Adverse events of immune-related etiology are expected because of the study drug's mechanism of action and may occur shortly after the first dose or several months after the last dose. Study treatment must be withheld if the patient experiences a drug-related toxicity or a severe or life-threatening AE.

A 4-hour observation period from the end of LY3435151 administration will occur in Cycles 1 and 2. During the observation period, patients treated with LY3435151 should be closely monitored for signs and symptoms indicative of an IRR by medical staff from the start of the infusion, in an area where emergency medical resuscitation equipment and other agents (eg, epinephrine, prednisolone, or equivalents) are available. LY3435151 IRRs will be defined according to the Common Terminology Criteria for Adverse Events (CTCAE), version 5.0 definition of IRRs.

The table below presents instructions for management of infusion-related reactions associated with LY3435151, pembrolizumab, or combination therapy.

Management of Infusion-Related Reactions

NCI CTCAE Grade	Treatment	Premedication at Subsequent Dosing

Grade 1
 
Mild reaction; infusion interruption not indicated; intervention not indicated
	
 Increase monitoring of vital signs as medically indicated until the participant is deemed medically stable in the opinion of the investigator. 	
None

Grade 2
 
Requires therapy or infusion interruption but responds promptly to symptomatic treatment (e.g., antihistamines, NSAIDs, narcotics, IV fluids); prophylactic medications indicated for ≤24 hrs.
	
 Stop Infusion. Additional appropriate medical therapy may include but is not limited to: 
 IV fluids Antihistamines NSAIDs Acetaminophen Narcotics Increase monitoring of vital signs as medically indicated until the participant is deemed medically stable in the opinion of the investigator. If symptoms resolve within 1 hour of stopping drug infusion, the infusion may be restarted at 50% of the original infusion rate (e.g. from 100 mL/hr. to 50 mL/hr.). Otherwise dosing will be held until symptoms resolve and the participant should be premedicated for the next scheduled dose. 
Participants who develop Grade 2 toxicity despite adequate premedication should be permanently discontinued from further study drug treatment
	
Participant may be premedicated 1.5 h (± 30 minutes) prior to infusion of LY3435151 or pembrolizumab with:
 
Diphenhydramine 50 mg PO (or equivalent dose of antihistamine).
 
Acetaminophen 500 to 1000 mg PO (or equivalent dose of analgesic).


Grades 3 or 4
 
Grade 3: Prolonged (i.e., not rapidly responsive to symptomatic medication and/or brief interruption of infusion); recurrence of symptoms following initial improvement; hospitalization indicated for other clinical sequelae (e.g., renal impairment, pulmonary infiltrates)
 
Grade 4: Life-threatening; pressor or ventilator support indicated
	
 • Stop Infusion. • Additional appropriate medical therapy may include but is not limited to: 
 • Epinephrine** • IV fluids • Antihistamines • NSAIDs • Acetaminophen • Narcotics • Oxygen • Pressors • Corticosteroids • Increase monitoring of vital signs as medically indicated until the participant is deemed medically stable in the opinion of the investigator. • Hospitalization may be indicated. 
**In cases of anaphylaxis, epinephrine should be used immediately.
 
Participant is permanently discontinued from further study drug treatment.
	
No subsequent dosing

Appropriate resuscitation equipment should be available at the bedside and a physician readily available during the period of drug administration. For further information, please refer to the CTCAE v5.0 at http://ctep.cancer.gov
		

If an IRR is clearly attributable to only one of the drugs, then the patient may continue to receive the other drug after consultation with the sponsor.

6.6.1. Dose Modification and Toxicity Management for Immune-Related AEs Associated with LY3435151, Pembrolizumab, or Combination Therapy

An irAE may be defined as an AE consistent with an immune-mediated chronic inflammatory reaction associated with drug exposure. These irAEs may occur shortly after the first dose or several months after the last dose of drug and may affect more than 1 body system simultaneously. Therefore, early recognition and initiation of treatment is critical to reduce complications. Based on existing clinical study data of immune checkpoint inhibitors, most irAEs are reversible and can be managed with interruptions of therapy, administration of corticosteroids, and/or other supportive care. For suspected irAEs, ensure adequate evaluation to confirm etiology or exclude other causes. Additional procedures or tests such as bronchoscopy, endoscopy, and skin biopsy may be included as part of the evaluation. Based on the severity of irAEs, withhold or permanently discontinue therapy and administer corticosteroids. Dose modification and toxicity management guidelines for potential irAEs are provided in the following table.

Dose Modification and Toxicity Management Guidelines for Immune-related AEs Associated with Study Treatment

General instructions:

1. Severe and life-threatening irAEs should be treated with IV corticosteroids followed by oral steroids. Other immunosuppressive treatment should begin if the irAEs are not controlled by corticosteroids.
2. Study treatment must be permanently discontinued if the irAE does not resolve or the corticosteroid dose is not ≤ 10 mg/day within 12 weeks of the last pembrolizumab or LY3435151 treatment.
3. The corticosteroid taper should begin when the irAE is \leq Grade 1 and continue at least 4 weeks.
4. If study treatment has been withheld, study treatment may resume after the irAE decreased to \leq Grade 1 after corticosteroid taper.

irAEs	Toxicity grade (CTCAE V5.0)	Action with study treatment	Corticosteroid and/or other therapies	Monitoring and follow-up
Pneumonitis	Grade 2	Withhold	
 • Administer corticosteroids (initial dose of 1 - 2 mg/kg prednisone or equivalent) followed by taper • Add prophylactic antibiotics for opportunistic infections 	
 • Monitor participants for signs and symptoms of pneumonitis • Evaluate participants with suspected pneumonitis with radiographic imaging and initiate corticosteroid treatment
	Recurrent Grade 2, Grade 3 or 4	Permanently discontinue		
Diarrhea / Colitis	Grade 2 or 3	Withhold	
 • Administer corticosteroids (initial dose of 1 - 2 mg/kg prednisone or equivalent) followed by taper 	
 • Monitor participants for signs and symptoms of enterocolitis (ie, diarrhea, abdominal pain, blood or mucus in stool with or without fever) and of bowel perforation (ie, peritoneal signs and ileus) • Participants with ≥Grade 2 diarrhea suspecting colitis should consider GI consultation and performing endoscopy to rule out colitis • Participants with diarrhea/colitis should be advised to drink liberal quantities of clear fluids. If sufficient oral fluid intake is not feasible, fluid and electrolytes should be substituted via IV infusion
	Recurrent Grade 3 or Grade 4	Permanently discontinue		

AST or ALT elevation or Increased Bilirubin	Grade 2 ^a	Withhold	
 Administer corticosteroids (initial dose of 0.5 - 1 mg/kg prednisone or equivalent) followed by taper 	
 Monitor with liver function tests (consider weekly or more frequently until liver enzyme value returned to baseline or is stable)
	Grade 3 ^b or 4 ^c	Permanently discontinue	
 Administer corticosteroids (initial dose of 1 - 2 mg/kg prednisone or equivalent) followed by taper 	
Type 1 diabetes mellitus (T1DM) or Hyperglycemia	New onset T1DM or Grade 3 or 4 hyperglycemia associated with evidence of β -cell failure	Withhold ^d	
 Initiate insulin replacement therapy for participants with T1DM Administer anti-hyperglycemic in participants with hyperglycemia 	
 Monitor participants for hyperglycemia or other signs and symptoms of diabetes
Hypophysitis	Grade 2	Withhold	
 Administer corticosteroids and initiate hormonal replacements as clinically indicated 	
 Monitor for signs and symptoms of hypophysitis (including hypopituitarism and adrenal insufficiency)
	Grade 3 or 4	Withhold or permanently discontinue ^d		
Hyperthyroidism	Grade 2	Continue	
 Treat with non-selective beta-blockers (eg, propranolol) or thionamides as appropriate 	
 Monitor for signs and symptoms of thyroid disorders
	Grade 3 or 4	Withhold or permanently discontinue ^d		
Hypothyroidism	Grade 2, 3, 4	Continue	
 Initiate thyroid replacement hormones (eg, levothyroxine or liothyronine) per standard of care 	
 Monitor for signs and symptoms of thyroid disorders
Nephritis: grading according to increased creatinine or acute kidney	Grade 2	Withhold	
 Administer corticosteroids (prednisone 1 – 2 mg/kg or equivalent) 	
 Monitor changes of renal function
	Grade 3 or 4	Permanently discontinue		

injury			followed by taper	
Myocarditis	Grade 1 or 2	Withhold	
 Based on severity of AE administer corticosteroids 	
 Ensure adequate evaluation to confirm etiology and/or exclude other causes
	Grade 3 or 4	Permanently discontinue		
All Other immune-related AEs	Persistent Grade 2	Withhold	
 Based on severity of AE administer corticosteroids 	
 Ensure adequate evaluation to confirm etiology or exclude other causes
	Grade 3	Withhold or discontinue based on the event ^e		
	Recurrent Grade 3 or Grade 4	Permanently discontinue		

^a AST/ALT: >3.0 - 5.0 x ULN if baseline normal; >3.0 - 5.0 x baseline, if baseline abnormal; bilirubin:>1.5 - 3.0 x ULN if baseline normal; >1.5 - 3.0 x baseline if baseline abnormal
 
^b AST/ALT: >5.0 to 20.0 x ULN, if baseline normal; >5.0 - 20.0 x baseline, if baseline abnormal; bilirubin:>3.0 - 10.0 x ULN if baseline normal; >3.0 - 10.0 x baseline if baseline abnormal
 
^c AST/ALT: >20.0 x ULN, if baseline normal; >20.0 x baseline, if baseline abnormal; bilirubin: >10.0 x ULN if baseline normal; >10.0 x baseline if baseline abnormal
 
^d The decision to withhold or permanently discontinue study treatment is at the discretion of the investigator or treating physician. If control achieved or ≤ Grade 2, study treatment may be resumed.
 
^e Events that require discontinuation include but are not limited to: Guillain-Barre Syndrome, encephalitis, Stevens-Johnson Syndrome and toxic epidermal necrolysis.
				

NOTE: The frequency or severity of known potential immune-related adverse events with pembrolizumab may be increased in combination with LY3435151. Therefore, particularly close monitoring for irAEs should be standard. For all irAEs of grade 2 or above, would consider specialist consultation and/or additional work-up including labs and biopsy to confirm diagnosis. For certain toxicities of more serious clinical consequence, such as myocarditis, neurologic, or ophthalmologic irAE, consider withholding therapy for grade 2 toxicities and early hospitalization for close monitoring for grade 3 toxicities. For any grade 2 or greater suspected irAE, please consult with Lilly CRS/CRP.

6.6.2. Dose Modification of Pembrolizumab

No dose reductions of pembrolizumab are permitted, but the dose may be withheld or discontinued for toxicity management. Guidelines for management of IRRs are located in Section 6.6 and for irAEs in Section 6.6.1.

6.6.3. Other allowed dose interruption for pembrolizumab

Pembrolizumab may be interrupted for situations other than treatment-related AEs such as medical / surgical events or logistical reasons not related to study therapy. Participants should be placed back on study therapy within 3 weeks of the scheduled interruption, unless otherwise discussed with the Sponsor. The reason for interruption should be documented in the patient's study record.

6.7. Intervention after the End of the Study

The end of study definition is provided in Section 4.4. Investigators will continue to follow the SoA (Section 1.3) until notified by Lilly that end of study has occurred.

6.7.1. Treatment after Study Completion

Study completion will occur following the final analysis of primary and secondary objectives, as determined by Lilly. Investigators will continue to follow the SoA (Section 1.3) for all patients until notified by Lilly that study completion has occurred.

6.7.1.1. Continued Access

Participants who are still on study intervention at the time of study completion may continue to receive study intervention if they are experiencing clinical benefit and no undue risks. The continued access period will apply to this study only if at least 1 participant is still receiving study intervention when study completion occurs. Lilly will notify investigators when the continued access period begins. Lilly may allow patients to enroll in a “rollover” protocol to provide long-term continued access for patients enrolled in this study.

The continued access period will begin after study completion and ends at End of Study. The participant’s continued access to study treatment will end when a criterion for discontinuation is met (Section 7). Continued access follow-up will begin when the participant and the investigator agree to discontinue study treatment. Follow-up procedures will be performed as shown in the SoA (Section 1.3).

Participants who are in short-term follow-up when the continued access period begins will continue in short-term follow-up until the short-term follow-up visit is completed. Long-term follow-up does not apply.

Participants who are in long-term follow-up when the continued access period begins will be discontinued from long-term follow-up.

7. Discontinuation of Study Intervention and Participant Discontinuation/Withdrawal

7.1. Discontinuation of Study Intervention

Possible reasons leading to permanent discontinuation of investigational product:

- **Participant Decision**
 - the participant or the participant's designee (for example, parents or legal guardian) requests to discontinue investigational product.

If a clinically significant finding is identified (including but not limited to changes from baseline in QTc using Fridericia's formula after enrollment, the investigator or qualified designee will determine if the participant can continue in the study and if any change in participant management is needed. This review of the ECG printed at the time of collection must be documented. Any new clinically relevant finding should be reported as an AE.

In addition, participants will be discontinued from the investigational product in the following circumstances:

- the patient becomes pregnant during the study
- the patient is significantly noncompliant with study procedures and/or treatment
- the patient, for any reason, requires treatment with another therapeutic agent that has been demonstrated to be effective for treatment of the study indication. Discontinuation from study treatment will occur prior to introduction of the new agent.
- the patient requires a dose delay of >21 days, excepted as described in Section 6.6.
- disease progression. Disease progression should be confirmed per iRECIST by the site 4 to 8 weeks after site-assessed first radiologic evidence of progressive disease in clinically stable participants. Participants, who have unconfirmed disease progression (iPUD) may continue on treatment at the discretion of the investigator until progression per iRECIST criteria is confirmed by the site. Patients continuing treatment in these circumstances must provide additional informed consent to continue therapy. A separate ICF will be created for this purpose. Any participant deemed clinically unstable should be discontinued from study treatment at first radiologic evidence of progressive disease and is not required to have repeat tumor imaging for confirmation of progressive disease by iRECIST.
- unacceptable toxicity
- the patient experiences a DLT or a DLT-equivalent toxicity
- occurrence of a venous thromboembolic event (DVT/PE) during the study
- the investigator decides that the patient should be discontinued from study treatment
- the patient experiences any of the following abnormal hepatic parameters, with the exception of patients who have existing liver metastases and elevated liver enzymes (>2×ULN) at baseline:
 - ALT or AST >8×ULN
 - ALT or AST >5×ULN for more than 1 week

- ALT or AST $>3\times$ ULN and (TBL $>2\times$ ULN or INR >1.5)
- ALT or AST $>3\times$ ULN with the appearance of fatigue, nausea, vomiting, right upper quadrant pain or tenderness, fever, rash, and/or eosinophilia
- Pembrolizumab will be discontinued after completion of approximately 2 years of treatment with pembrolizumab (completion of 35 treatments with pembrolizumab)

Note: The number of treatments is calculated starting with the first dose of pembrolizumab in Study JZIA.

Participants discontinuing from the investigational product prematurely for any reason should complete AE and other follow-up procedures per Section 1.3 (Schedule of Activities), Section 8.3 (Adverse Events and Serious Adverse Events), and Section 8.2 (Safety Assessments) of the protocol.

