4.1.1.2. Dose-Limiting Toxicity Determination

A DLT is defined as any of the events listed in the table below if the event occurs during the DLT observation period (2 Cycles/42 days for Cohorts A1-A6 and B1-B2) in Phase 1a, and toxicity that is not clearly and directly related to the primary disease or another etiology.

Patients who experience a DLT in the DLT observation period will be discontinued from study treatment.

Dose-Limiting Toxicities of Study Treatment

Hematologic Toxicity

 • Grade 3 thrombocytopenia associated with clinically significant bleeding and /or requiring platelet transfusion or Grade 4 thrombocytopenia of any duration • Grade ≥ 3 febrile neutropenia and/or neutropenia requiring G-CSF • Grade ≥ 4 neutropenia lasting >7 days • Grade ≥ 3 anemia requiring a blood transfusion • Other Grade 4 toxicity lasting >7 days, excluding toxicities listed below and Grade 3 endocrine irAEs that can be managed by steroids or hormone replacement therapy
Nonhematologic Toxicity – Nonlaboratory

 • Grade 4 AE (unless stated otherwise below) • Any Grade ≥ 3 colitis or noninfectious pneumonitis irrespective of duration • Any other Grade 3 AE, excluding toxicities listed below • Grade ≥ 3 toxicity lasting >7 days despite optimal supportive care • Other Grade 2 irAE, excluding colitis or pneumonitis, that:

 ○ does not downgrade to Grade 1 within 3 days after onset of the event despite optimal medical management including corticosteroid therapy, or ○ does not downgrade to Grade 1 or the patient's baseline level within 14 days after onset of the event
Nonhematologic Toxicity – Laboratory/Investigations

 • Grade 3 or 4 laboratory value if: 
 ○ Medical intervention or hospitalization is required to treat the patient, or ○ The abnormality persists for >7 days (excluding amylase and lipase) • ALT or AST: 
 ○ >8 × ULN ○ ≥2-fold above the patient's baseline value that lasts >7 days, if the patient has HCC or liver metastasis and had ALT or AST >3.0 × ULN at baseline ○ ≥3 × ULN with concomitant bilirubin >2 × ULN, in the absence of cholestasis • Total bilirubin >3 × ULN • Grade ≥3 amylase or lipase that is associated with symptoms or clinical manifestations of pancreatitis
Other Hematologic or Nonhematologic Toxicity

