4.1.1.3. DLT-Equivalent Toxicities

A DLT-equivalent toxicity (ET) is an AE that meets the DLT criteria as defined above and occurs in any cycle other than the DLT assessment period for cohorts in Phase 1a (42 days for Cohorts A1-A6 and B1-B2) and occurs in any cycle for cohorts in Phase 1b. In addition to the DLT assessment period, available safety data beyond the DLT assessment period may also be taken into consideration prior to a decision to advance to the next dose level or the determination of the RP2D.

For individuals experiencing a DLT-ET, dose modifications can be made as outlined in Section 6.6. If cumulative incidence of DLT-ET is 30% at any point during study, re-evaluation of dose will occur.

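### Section 7.1 requires study drug to be stopped for any DLT-equivalent toxicity, while Sections 4.1.1.3, 6.6 and 6.6.1 allow the same event to be managed by delaying, withholding or continuing treatment.

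*Protocol*

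**What the plan says.** A DLT-equivalent toxicity (Protocol 4.1.1.3) is an AE that meets the DLT criteria and "occurs in any cycle other than the DLT assessment period for cohorts in Phase 1a", or that occurs in any cycle of Phase 1b. Four places then bear on treatment.

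- **Section 7.1** lists circumstances in which the participant is to come off investigational product, in mandatory terms. One is that "the patient experiences a DLT or a DLT-equivalent toxicity". A neighbouring bullet on long delays does carry an exception: "the patient requires a dose delay of >21 days, excepted as described in Section 6.6".
- **Section 4.1.1.3** is permissive: "For individuals experiencing a DLT-ET, dose modifications can be made as outlined in Section 6.6".
- **Section 6.6** says: "After the DLT observation period, doses of the LY3435151 or pembrolizumab may be delayed, omitted, or discontinued to manage specific AEs or other toxicities". It also says: "Starting at Cycle 3, dose delays will be permitted. See Section 7 for discontinuation criteria", and separately: "Study treatment must be withheld if the patient experiences a drug-related toxicity or a severe or life-threatening AE".
- **Section 6.6.1** assigns an action to each type and grade of immune-related AE (irAE): continue, withhold, withhold or discontinue, or permanently discontinue. Its general instructions let withheld treatment resume once the event has improved to Grade 1 or lower after the steroid taper.

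For a DLT inside the 42-day observation period, Sections 4.1.1.2 and 7.1 agree that treatment stops.

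**The concern.** The DLT-equivalent bullet in 7.1 and the sentence in 4.1.1.3 concern the same event and give it different consequences. A site that follows 7.1 stops the drug. A site that follows 4.1.1.3 into 6.6 and 6.6.1 may delay it, withhold and resume it, or carry on.

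The first thing at stake is patient safety: the choice decides who stays on study drug after a serious toxicity. The second is the safety analysis, which is the primary objective. SAP 5.4.7 summarises AEs leading to delay or omission separately from AEs leading to discontinuation, so an identical event would fall in one or the other according to how the site read the protocol. Dose intensity (SAP 5.4.6) would move with it. Choice of the RP2D draws on dose adjustments and chronic intolerance (4.1.1.4), may use safety data from beyond the DLT window (4.1.1.3), and may be revisited on expansion safety data (9.2).

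**Working it through.** This is a comparison of passages. Arithmetic enters only for the liver thresholds and the scope.

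**Step 1. Find events that meet a DLT criterion (4.1.1.2) and have a non-stopping action in 6.6.1.**

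| Event outside the Phase 1a DLT period | Why it meets a DLT criterion | Section 7.1 | Section 6.6.1 |
|---|---|---|---|
| First Grade 3 colitis | Grade 3 or higher "colitis or noninfectious pneumonitis irrespective of duration" | Stop | Withhold; permanent stop kept for recurrent Grade 3 or for Grade 4 |
| ALT/AST and bilirubin raised together (Step 2) | Combined liver criterion, no cholestasis | Stop, under two bullets | Withhold (Grade 2 row) |
| Grade 4 hypothyroidism | Grade 4 AE; the endocrine exemption covers Grade 3 only | Stop | Continue |
| Grade 2 irAE, other than colitis or pneumonitis, that does not downgrade in time | Persistent Grade 2 criterion (3-day or 14-day limit) | Stop | Withhold in most rows; continue in both thyroid rows |

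For Grade 4 hypothyroidism there is a further text. If the event is drug-related or life-threatening, 6.6 says treatment must be withheld, which also contradicts the table's instruction to continue.

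**Step 2. Liver overlap, normal baseline.**

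- ALT/AST: DLT criterion ≥3 × ULN; 7.1 hepatic bullet >3 × ULN; 6.6.1 Grade 2 row >3.0 to 5.0 × ULN. Intersection: >3.0 to 5.0 × ULN.
- Bilirubin: DLT criterion >2 × ULN; 7.1 hepatic bullet >2 × ULN; 6.6.1 Grade 2 row >1.5 to 3.0 × ULN. Intersection: >2.0 to 3.0 × ULN.

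For example, ALT 4 × ULN with bilirubin 2.5 × ULN is Grade 2 on both parameters, so the table says withhold. The same values trigger the DLT-equivalent bullet and, independently, the hepatic bullet in 7.1.

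**Step 3. Do the cross-references settle it?** Section 6.6 points to Section 7 for discontinuation criteria but does not say that Section 7 overrides 4.1.1.3. If 7.1 always governed, the dose-modification sentence in 4.1.1.3 would have almost no effect. Conversely, 7.1 writes a 6.6 exception into its delay bullet and not into the DLT-equivalent bullet, so an exception cannot be assumed there.

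**Step 4. Scope.** Phase 1b: 2 × (16 + 32) + 30 = 126 patients. 126 / 170 = 0.74. Phase 1a patients still treated after Day 42 come on top.

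**The case against.** The strongest reply is that most of these passages can be satisfied together. Resumption after withholding is optional, so a site that withholds and then stops under 7.1 breaches neither text. On that view only the continue rows are strict contradictions. Part of this stands. Rows reading withhold or discontinue do not conflict with 7.1, and for Grade 4 hypothyroidism stopping also satisfies the 6.6 instruction to withhold, so the real split is stop or withhold against continue. It does not dispose of colitis, because that row treats withholding and permanent discontinuation as separate actions and reserves the second for recurrent Grade 3 or for Grade 4.

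A second reply is that the liver row grades each parameter separately, while 7.1 addresses the combination. A specific rule could be read alongside a general one, but the protocol does not say so, and the Step 2 example is Grade 2 on both parameters.

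A third is that 4.1.1.3 keeps some role under 7.1, because the synopsis lets a patient taken off one drug continue the other, and 110 of the 126 Phase 1b patients (40 + 40 + 30) receive both. This is arguable, but the 7.1 bullet does not say which drug it covers.

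Finally, 6.6.1 asks sites to consult the sponsor on suspected irAEs of Grade 2 or higher, and Section 8 sends immediate safety concerns to the sponsor. This gives a route for individual cases but no order of precedence. It is also true that DLT-equivalent AEs have their own summary whatever action was taken, so no event is lost from reporting. The table also agrees with 7.1 for Grade 3 or 4 pneumonitis, liver events, nephritis and myocarditis.

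**Conclusion.** The conflict is real and the protocol does not resolve it. A mandatory stop in 7.1 stands against a permissive instruction in 4.1.1.3 and 6.6. In 6.6.1 it becomes a concrete difference for first Grade 3 colitis, combined liver elevation in the overlap range, Grade 4 hypothyroidism and persistent Grade 2 irAEs.

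The 126 patients (74%) are those to whom the rule applies, not those expected to be affected. The documents give no rate for DLT-equivalent events. The liver case assumes normal baseline values, no cholestasis and an event handled under the irAE table.

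The mTPI-2 DLT counts do not change, and neither does the 30% re-evaluation trigger in 4.1.1.3, which counts incidence rather than action taken. Because the instructions concern whether patients stay on drug after serious toxicity, this must be corrected in the protocol.

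**What to change.** Reconcile the DLT-equivalent and hepatic bullets of 7.1 with 4.1.1.3, 6.6 and every 6.6.1 row in which an event can meet a DLT criterion, persistent Grade 2 irAEs included, so that each event has one treatment consequence. State which section governs. If 6.6 and 6.6.1 are meant to apply, the 7.1 bullet should carry the exception, as its delay bullet does. If 7.1 is meant to govern, 4.1.1.3 and 6.6.1 should say so. For combination patients, say whether the rule applies to one drug or both. The clinical rule itself is for the sponsor to decide.

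The cost is one protocol wording amendment, with the ethics approval that Appendix 1 requires for amendments, and matching site and eCRF guidance. It needs no SAP change, no added procedures and no added patients.
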